#### 10.3 POTENTIAL DISTANT SPREAD OF TOXIN ADVERSE EVENTS

All TEAEs associated with PDSOT will be tabulated by preferred term, and treatment group; in addition, all PDSOT TEAEs will be listed by subject.

#### 10.4 ADVERSE EVENTS OF SPECIAL INTEREST

An adverse event of special interest (AESI) is a TEAE which may warrant ongoing monitoring. The following MedDRA preferred terms are considered AESI in this study:

- facial paralysis
- Bell's palsy

These AESIs will be summarized by preferred term and treatment group.

## 10.5 VITAL SIGNS

Descriptive statistics for vital signs (systolic and diastolic blood pressures, respiratory rate, pulse rate, and weight) values at baseline, postbaseline, and changes from baseline values at each postbaseline timepoint will be presented by treatment group.

# 11.0 HEALTH OUTCOMES ANALYSES

All data collected from questionnaires are discussed in the efficacy analyses (see Section 9.0).

## 12.0 SUBGROUP ANALYSES

# 13.0 INTERIM ANALYSIS

No interim analysis is planned for this study.

## 14.0 OVERALL TYPE-I ERROR CONTROL

The overall familywise error rate (FWER) will be controlled at  $\alpha = 0.05$  for the set of primary and secondary endpoint comparisons between BOTOX 72 U vs placebo.

The overall serial gatekeeping multiple comparisons procedure (MCP) is defined in Table 5.

## 15.0 DETERMINATION OF SAMPLE SIZE

approximately 360 participants (270 BOTOX and 90 placebo) will provide

> 90% power

[figure not shown]
# 16.0 STATISTICAL SOFTWARE

Statistical analyses will be performed using version 9.4 (or newer) of SAS.

## 17.0 DATA HANDLING CONVENTIONS

## 17.1 VISIT TIME WINDOWS

For efficacy and safety analyses, the following visit windows will be used to determine the visit day assignment, based on the observed number of days relative to the start of each treatment cycle (the day of treatment).

If the assessment date is on or after the date of the first dose of study treatment, the study day is calculated by assessment date – date of the first dose of study treatment + 1. If the assessment date is before the date of the first dose of study treatment, the study day is calculated by assessment date – date of the first dose of study treatment. Therefore, a negative day indicates a day before the start of the study treatment. If the assessment date is unavailable, use the visit date instead.

If there are values from multiple visits in a given window, the value collected from the visit closest to the target day will be used to represent the window. If 2 visits are equidistant from the

target day, the value from the first scheduled visit of the 2 visits chronologically will be used to represent the window.

#### 17.2 TREATMENT CYCLES

A treatment cycle is considered to start on the day of treatment with study medication and end on the day prior to the next study treatment or on the study exit day if there are no subsequent treatments.

[figure not shown]

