Danied 2 (Davis 190 through 540/Study Evit)

Period 2 (Days 180 through 540/Study Exit)

Day 180 is considered both the end of Period 1 and the beginning of Period 2. After Period 1 assessments are collected, the participant will enter Period 2 and will be assessed for retreatment. If the participant does not meet the retreatment criteria at Day 180, he or she will be reassessed at the next visit. All BOTOX and placebo-treated participants from Period 1 are eligible to receive up to 2 open-label treatments of BOTOX 72 U in Period 2 *if* they meet the following retreatment criteria (also see Section 6.6) on or after the Day 180 visit.

- Participant has bilateral marked (Grade 4) or very marked (Grade 5) MMP, as assessed by the investigator using the MMPS, AND
- Females of childbearing potential must have a negative pregnancy test prior to treatment,
 AND
- If it is the third treatment, at least 3 months have lapsed since the previous study treatment (no retreatment earlier than 84 days)

During Period 2, participants will attend all follow-up visits (Days 210, 240, 270, 300, 330, 360, 390, 420, 450, 480, 510, and 540). For Treatment 2, participants who qualify can be retreated from the Day 180 visit through the Day 420 visit. For Treatment 3, the earliest visit that participants may qualify and receive the third treatment is Day 270 (3 months after the earliest visit for Treatment 2 [Day 180]). The last day that a participant can receive either Treatment 2 or 3 is Day 420; this ensures a 120-day safety and efficacy follow-up period by Day 540/study exit. A participant who meets retreatment criteria may decline retreatment if they choose, and their reason will be captured on the eCRF. If the participant still meets retreatment criteria at the next visit (up to Day 420), he or she may receive retreatment at that time.

In Period 2, participants will receive up to 2 additional treatments. Based on individual variability in time to meet retreatment criteria noted in the Phase 2 Study 191622-130, retreatment timepoints are not expected to be synchronized among the participants in the study.

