## 4.0 INTRODUCTION

This statistical analysis plan (SAP) provides a more technical and detailed elaboration of the statistical analyses of the efficacy and safety data as outlined and/or specified in the final protocol of Study 1789-301-008 (version dated 17 Dec 2018). Specifications of tables, figures, and data listings are contained in a separate document.

This is an 18-month, multicenter study consisting of 2 periods, a double-blind placebo-controlled single-treatment period and an open-label period in which a maximum of 2 further study treatments can be received. Up to 20 scheduled visits are planned: screening (Day -14 to Day -1), baseline (Day 1), follow-up monthly thereafter (Days 30, 60, 90, 120, 150, 180, 210, 240, 270, 300, 330, 360, 390, 420, 450, 480, 510), and study exit (Day 540).

Period 1 (Days 1 through 180) will be a double-blind, randomized, placebo-controlled, single-treatment design, which will assess the safety and efficacy of botulinum toxin type A purified neurotoxin (BOTOX) treatment of masseter muscle prominence (MMP). On Day 1, participants will be randomized in a 3:1 ratio to receive BOTOX 72 unit (U) or placebo. Randomization will be stratified at each investigator site by the participant's baseline Masseter Muscle Prominence Scale (MMPS) Grade (4 or 5). On Day 180, final Period 1 assessments will be collected, after which all participants will continue into Period 2, the open-label treatment portion of the study.

Period 2 (Days 180 through 540) will be open-label. All BOTOX and placebo-treated participants from Period 1 are eligible to receive up to 2 open-label treatments of BOTOX 72 U in Period 2 if they meet protocol-specified retreatment criteria on or after the Day 180 visit. If the participant does not meet the retreatment criteria at the Day 180 visit, he or she will be reassessed at the next visit. For Treatment 2, participants who qualify can be retreated from the Day 180 visit through the Day 420 visit.

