## 9.0 EFFICACY ANALYSES

The efficacy analyses will be based on the mITT population. Baseline for efficacy is defined as the last approved (imaging data) non-missing efficacy assessment before the first dose of study treatment. Pairwise comparisons will be conducted between BOTOX 72 U group and the placebo group. All statistical tests will be 2-sided hypothesis tests performed at 5% level of significance for main effects, with Type I error controlled as described further in Section 14.0.

For the primary and secondary efficacy variables, subjects with missing values at a given visit will be imputed using multiple imputation (MI) up to Day 180 in Period 1. The other efficacy variables will not be imputed.

For subjects who continue in Period 2, efficacy visits beyond Day 180 but prior to retreatment (if any) will be displayed by assigned treatment group in double-blind treatment cycle 1.

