## 9.2 SECONDARY EFFICACY ENDPOINTS

The secondary efficacy endpoints are:

- Achievement of MMPS Grade ≤ 3 at Day 90, according to investigator
- Achievement of MMPS-P Grade ≤ 3 at Day 90, according to participant
- Achievement of ≥ 2-grade improvement from baseline at Day 90 using the MMPS-P
- Achievement of PSAC Grade ≥ 1 (at least minimally improved from baseline) at Day 90
- Change from baseline in lower facial width (mm) at Day 90

Duration of effect for BOTOX-treated MMPS responders

The proportion of participants who achieve MMPS Grade  $\leq$  3, the proportion of participants who achieve MMPS-P Grade  $\leq$  3, the proportion of participants who achieve  $\geq$  2-grade improvement from baseline using the MMPS-P, and the proportion of participants who achieve PSAC Grade  $\geq$  1 will be analyzed in the same manner as that used to analyze the primary endpoint. Missing MMPS, MMPS-P, and PSAC values in Period 1 will be imputed using the same MI method as for primary endpoint.

Table 3. Summary of the Estimand Attributes of the Secondary Efficacy Endpoints

	Attributes of the Estimand								
Estimand Label	Treat- ment	Endpoint	Population	Handling of Intercurrent Events	Statistical Summary				
Hypothetical estimand for binary secondary endpoints	BOTOX 72 U vs placebo	Achievement of the following at Day 90:  • MMPS Grade ≤ 3  • MMPS-P Grade ≤ 3  • MMPS-P ≥ 2-grade improvement from baseline  • PSAC Grade ≥ 1	mITT (all randomized participants with at least one postbaseline MMPS assessment)	Participants who discontinue prior to Day 90 assessments or who do not have specified Day 90 secondary efficacy assessments will be included in the analysis as a hypothetical scenario in which they had not missed the assessments	Difference in response proportions between treatments after MI using CMH test stratified by baseline MMPS				
Hypothetical estimand for continuous secondary endpoints	BOTOX 72 U vs placebo	Change from baseline in lower facial width (mm) at Day 90	mITT (all randomized participants with at least one postbaseline MMPS assessment)	Participants who discontinue prior to Day 90 assessments or who do not have Day 90 lower facial width will be included in the analysis as a hypothetical scenario in which they had not missed the lower facial width assessments	Difference between treatments in LS Mean and SE after MI using ANCOVA				

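### SAP 17.2's date-based cycle boundary conflicts with Day 180 being the final Period 1 assessment; applied literally, it would drop observed non-responses and bias Day 180 responder rates upward in both arms

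*SAP*

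**What the plan says.** SAP 17.2 sets the boundary by calendar day: "A treatment cycle is considered to start on the day of treatment with study medication and end on the day prior to the next study" (meaning the next injection). Without a further treatment, the cycle runs to study exit. SAP 17.1 assigns assessments to visit windows "based on the observed number of days relative to the start of each treatment cycle (the day of treatment", and it computes study day from dates, not clock times.

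Other sections treat Day 180 differently. Protocol 4.1 states "Day 180 is considered both the end of Period 1 and the beginning of Period 2" and gives the order of events: "After Period 1 assessments are collected, the participant will enter Period 2 and will be assessed for" retreatment. SAP 4.0 agrees: "On Day 180, final Period 1 assessments will be collected, after which all participants will continue into Period 2".

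SAP 9.0 says that, for primary and secondary variables, "subjects with missing values at a given visit will be imputed using multiple imputation (MI) up to Day 180 in Period 1". It also displays efficacy visits later than Day 180 and before any retreatment under the cycle 1 group; SAP 10.0 has a parallel rule for safety data. SAP 9.1 plans the stratified CMH comparison at every visit, so Day 180 responder rates are a planned output. SAP 9.2 lists "Duration of effect for BOTOX-treated MMPS responders" as a secondary endpoint. Its event and censoring rules are not visible.

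**The concern.** Retreatment is given at the scheduled visit where the investigator grades the participant, and SAP Table 1 schedules the MMPS, MMPS-P, PSAC and imaging at those same visits. Every retreatment date should therefore carry an efficacy assessment made before the injection. Under 17.2 that assessment carries a date belonging to the next cycle.

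The values affected are not a random subset. Retreatment requires MMPS Grade 4 or worse on each side. Baseline is Grade 4 or 5, so such a participant has improved by at most one grade and fails both MMPS definitions (Grade ≤ 3 and ≥ 2-grade improvement). If these values were removed from cycle 1, Day 180 would be missing because of the Day 180 grade itself. Imputation from earlier visits cannot in general recover that.

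At stake are the responder rates at the last placebo-controlled visit and, possibly, duration of effect. Two programmers could follow different sections of the SAP and report materially different Day 180 rates.

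**Working it through.** **Stated figures.** The plan gives no Day 180 rate, retreatment uptake or duration to reproduce. All rates below are assumptions.

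**Step 1: boundary.** With retreatment on study day D, the last day of cycle 1 is D − 1. The Day 180 visit window is ± 7 days (SAP Table 1), so D = 173, 180 or 187 gives a last cycle 1 day of 172, 179 or 186. The same-date value taken before the injection lies outside cycle 1 in each case.

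**Step 2: the passages compared.** Protocol 4.1 and SAP 4.0 speak of periods and put the Day 180 values in Period 1. SAP 17.1 and 17.2 speak of cycles and, by date, put the same values in cycle 2. The carry-forward rule in SAP 9.0 covers visits after Day 180, not Day 180 itself. For a later retreatment visit, an assessment before the injection precedes retreatment by the clock but not by date.

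**Step 3: Day 180 rate without imputation.** Let r be the true MMPS responder rate and q the share of non-responders retreated that day. If their values are dropped:

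apparent rate = r / [r + (1 − r)(1 − q)]

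- r = 30%: 36%, 46% and 63% for q = 25%, 50% and 75%. For example, 0.30 / (0.30 + 0.70 × 0.50) = 0.46.
- r = 10%: 13%, 18% and 31% for the same q.

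**Step 4: Day 180 Grade ≤ 3 rate with imputation from Day 150 status.** Assumed for placebo: 10% responders at Day 150, of whom 70% keep response, and 4% of the others gain it. Assumed for BOTOX: 75%, 80% and 5%. The same q applies whatever the Day 150 status.

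- True placebo: 0.10 × 0.70 + 0.90 × 0.04 = 10.6%.
- True BOTOX: 0.75 × 0.80 + 0.25 × 0.05 = 61.3%.

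With values dropped, a conditional response probability p becomes p / [p + (1 − p)(1 − q)]. At q = 90%:

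- Placebo: 0.70 becomes 0.70/0.73 = 0.959, and 0.04 becomes 0.04/0.136 = 0.294. Imputed rate: 0.10 × 0.959 + 0.90 × 0.294 = 36.1%.
- BOTOX: 0.80 becomes 0.80/0.82 = 0.976, and 0.05 becomes 0.05/0.145 = 0.345. Imputed rate: 0.75 × 0.976 + 0.25 × 0.345 = 81.8%.

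| | Placebo | BOTOX | Difference |
|---|---|---|---|
| True | 10.6% | 61.3% | 50.7 points |
| q = 70% | 19.8% | 73.5% | 53.7 points |
| q = 90% | 36.1% | 81.8% | 45.7 points |

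Both arms rise. The difference moves up about 3 points or down about 5.

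**Step 5: duration, only if it is read from cycle 1 records.** Simulation assumptions: Weibull shape 2, loss no earlier than day 91, visits every 30 days. Losses found at Days 180 to 420 and retreated at that visit are censored the day before.

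- True median 180 days: with 50%, 80% and 100% same-visit retreatment, 30%, 48% and 60% of loss events become censored. The Kaplan-Meier median reads 210, 270 and 450 days.
- True median 270 days (270 to 300 at visit resolution): 33%, 53% and 66% become censored. The median reads 360, 450 and 480 days.

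**The case against.** The best defence is that the plan already settles Day 180. Both documents call these values the final Period 1 assessments, the protocol has them collected before the retreatment decision, and SAP 9.0 imputes only missing values; an observed value is not missing. SAP 17.3 also shows that the SAP does not work by date alone: it takes the first baseline from before the injection, on Day 1 if available, and recognises a cycle baseline. In addition, the window table, the material after the 17.2 sentence, the imputation model and the duration definition are not visible, and any of them might carry the missing rule.

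Much of this stands. A reader might infer that the plan does inflate Day 180 response. The documents do not support that, because the bias arises only if 17.2 is allowed to override the Period 1 wording. A reader might also infer that duration of effect is overstated. That cannot be shown: the derivation could run from Day 1 across all visits and count the relapse seen at the retreatment visit. Nor do the figures show an exaggerated treatment effect, since the Day 180 difference has no consistent direction.

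What the defence does not remove is the conflict. The visible 17.2 rule is explicit, 17.1 is anchored to it, and no visible sentence subordinates either to the Period 1 description. The exception written for the first injection is not written for later ones.

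**Conclusion.** The point holds as an unreconciled conflict with a conditional consequence. Read by date, SAP 17.1 and 17.2 assign efficacy values taken before a retreatment injection to the next cycle; Protocol 4.1 and SAP 4.0 place the Day 180 values in Period 1. If the cycle rule is programmed literally, observed MMPS non-responses at Day 180 become imputed values, and MMPS responder rates are biased upward in both arms.

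The size rests wholly on assumed response rates, uptake and a Day 150 imputation model. In the examples the imputed rates rise by about 9 to 25 points on placebo (10.6% to 19.8% or 36.1%) and about 12 to 21 on BOTOX (61.3% to 73.5% or 81.8%). For MMPS-P, PSAC and facial width the values would also move, but retreatment does not select on them directly, so no size is claimed.

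The primary endpoint and the Day 90 secondary endpoints are unaffected, because no retreatment occurs before the Day 180 visit. Duration of effect is a risk to check, not a demonstrated error.

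**What to change.** Amend SAP 17.2, with a matching line in 17.1, along these lines: efficacy assessments made before the injection on a retreatment date belong to the cycle being closed and may also serve as the baseline of the next cycle; observed Day 180 values taken before an injection are the cycle 1 Day 180 values and are not imputed.

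Confirm that the duration-of-effect derivation uses the value recorded at the retreatment visit. If text that is not visible already does so, a cross-reference from 17.2 is enough.

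For adverse events on a retreatment date, use the collection before and after treatment already required by SAP Table 1 (footnote m), and state a default cycle for events whose onset time is unknown. SAP 17.9 and 17.10 already allow that time may not be known.

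The cost is a few sentences and one programming rule. No new efficacy data are needed, and no retreatment rule changes.

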# 17.3 BASELINE, CHANGE FROM BASELINE, AND DIRECTION OF DIFFERENCES

[figure not shown]
The latest measurement taken on or before day 1 prior to the first injection will be the baseline measurement. Changes from baseline will be based on the day 1 baseline (rather than cycle baseline) unless otherwise stated.

Change from baseline will be calculated as postbaseline minus baseline. The interpretation of a positive or negative change from baseline is specific to the outcome measure and will be discussed as needed. Treatment differences will be reported as BOTOX minus placebo.

#### 17.4 STRATIFICATION

Randomization is stratified by baseline MMPS (4 or 5) at baseline (day 1). In case of misstratification, the subjects' actual baseline MMPS will be used for analyses.

# Participant Self-Assessment of Change (PSAC)

The participant will answer the questions on the accompanying assessments via electronic tablet that will be provided to the study participant at the study site.

[figure not shown]
## Lower Facial Width

The lower facial width (mm) will be calculated from 2D projections of 3D images.

## 17.6.2 Other Efficacy Assessments

If a participant has repeated assessments before the start of the first treatment, the results from the final nonmissing assessment made prior to the start of the study treatment will be used as baseline. If end-of-study assessments are repeated or if unscheduled visits occur, the last nonmissing postbaseline assessment will be used as the end-of-study assessment for generating summary statistics. However, all postbaseline assessments will be used for PCS value determinations, and all assessments will be presented in the data listings.

#### 17.8 MISSING DATE OF THE LAST DOSE OF STUDY TREATMENT

When the date of the last dose of study treatment is missing for a participant in the Safety Population, all efforts should be made to obtain the date from the Investigator. If after all efforts are made it is still missing, the last available dosing record date will be used as the last dose date.

#### 17.9 MISSING SEVERITY ASSESSMENT FOR ADVERSE EVENTS

If severity is missing for an AE that started before the date of the first dose of study intervention, an intensity of mild will be assigned. If severity is missing for an AE that started on or after the date of the first dose of study intervention (based on date, and time if known), an intensity of severe will be assigned. The imputed values for severity assessment will be used for the incidence summary; the values will be shown as missing in the data listings.

# 17.10 MISSING CAUSAL RELATIONSHIP TO STUDY DRUG FOR ADVERSE EVENTS

If the causal relationship to study intervention is missing for an AE that started before first dose of study intervention, a causality of no will be assigned. If the causal relationship to the study intervention (per the investigator) is missing for an AE that started on or after the date of the first dose of study intervention (based on date, and time if known), a causality of yes will be assigned. The imputed values for causal relationship to study intervention will be used for the incidence summary; the values will be shown as missing in the data listings.

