8.3.3. Follow-up of Adverse Events and Serious Adverse Events

After the initial AE/SAE report, the investigator is required to proactively follow each participant at subsequent visits/contacts. All SAEs and any AESI as defined in Appendix 2 will be followed

CONFIDENTIAL Protocol 1789-301-008

BOTOX

until resolution, stabilization, the event is otherwise explained, or the participant is lost to followup (as defined in Section 7.3).

The investigator is obligated to perform or arrange for the conduct of supplemental measurements and/or evaluations as medically indicated or as requested by the sponsor to elucidate the nature and/or causality of the AE or SAE as fully as possible. This may include additional laboratory tests or investigations, histopathological examinations, or consultation with other health care professionals. If a participant dies during participation in the study, the investigator will provide the sponsor with a copy of any postmortem findings including histopathology.

New or updated information will be recorded in the originally completed eCRF.

The investigator will submit any updated SAE data to the sponsor within 24 hours of receipt of the information.

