#### 10.2 ADVERSE EVENTS

Adverse events will be coded by system organ class and preferred term using the *Medical Dictionary for Regulatory Activities*, version 25.1 or newer.

An AE will be considered as a treatment-emergent adverse event (TEAE) if the AE began or worsened (increased in severity or became serious) on or after the date of the first dose of double-blind study treatment.

A TEAE for treatment cycle 1 is an adverse event with onset after the initiation of study treatment or became serious after the initiation of study treatment for cycle 1.

In each of the analysis periods (treatment cycle 1 in the double-blind period, open-label period, BOTOX cycle, or BOTOX overall), a specific TEAE will only count once per participant, associated with its worst severity during the time period of interest. Unless stated otherwise, the methods of analyses described in this section will be applied to each of the study period.

TEAEs will be summarized for each treatment group by treatment cycle 1 in the double-blind period, open-label period, by BOTOX cycle, and BOTOX exposure overall. Participants will be counted according to the treatment received at baseline (Placebo or BOTOX 72 U) for treatment cycle 1. For open-label period and Any BOTOX exposure tables, participants will be summarized according to the treatment received at cycle 1 baseline and treatment received during open-label (Placebo/BOTOX 72 U or BOTOX 72 U/BOTOX 72 U and Total). The only

exception is BOTOX cycle 3, where participants will be summarized by BOTOX 72 U/BOTOX 72 U.

Overall summary of AEs will be provided on a per-participant basis for categories of TEAEs, treatment-related TEAEs, deaths, serious adverse events (SAEs), AEs leading to discontinuation, and possible distant spread of toxin (PDSOT).

The number and percentage of participants reporting TEAEs in each treatment group will be tabulated by system organ class (SOC) and preferred term, and further categorized by severity and causal relationship to the study treatment separately. If more than 1 AE is coded to the same preferred term for the same participant, the participant will be counted only once for that preferred term using the greatest severity and strictest causality for the summarization by severity and causal relationship.

The incidence of TEAEs will be summarized by preferred term and treatment.

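### SAP 17.9 and 17.10 impute missing AE severity and causality from the start date alone, which does not match the treatment-emergent definition in SAP 10.2 and Protocol 9.4.2.1

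*SAP*

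**What the plan says.** **Imputation rules.** SAP 17.10 states that, where causality is missing, "for an AE that started before first dose of study intervention, a causality of no will be assigned". For an AE starting on or after the first dose, "a causality of yes will be assigned". SAP 17.9 follows the same pattern for severity: "for an AE that started before the date of the first dose of study intervention, an intensity of mild will be assigned", and for a later start "an intensity of severe will be assigned". Both sections send the imputed value to the incidence tables and leave the field shown as missing in the listings. Neither makes an exception to the start-date split.

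**Treatment-emergent definition.** The condition for a TEAE in SAP 10.2 is that "the AE began or worsened (increased in severity or became serious) on or after the date of the first dose of double-blind study treatment". Protocol 9.4.2.1 says the same and makes explicit that the AE may already be present before dosing. A second sentence in SAP 10.2, for treatment cycle 1, names onset and becoming serious but not an increase in severity.

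**Tables affected.** SAP 10.2 breaks TEAEs down by severity and by relationship to treatment. Protocol 9.4.2.1 adds a separate table of treatment-related TEAEs.

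**Recording.** Protocol 8.3.1 collects AEs from consent, so the database will hold events that began before dosing. Protocol 8.3.3 says of follow-up: "New or updated information will be recorded in the originally completed eCRF".

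**The concern.** The two rules appear to treat start date and treatment-emergent status as the same thing, and they are not. Assigning not related to an event that began before dosing is sensible while the event stays a pretreatment AE, since treatment cannot have caused its onset. Once the event worsens or becomes serious after dosing, the plan itself counts it as treatment-emergent. The question is then whether treatment contributed to the change, and the start date no longer answers it.

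Elsewhere the SAP resolves uncertainty about AEs conservatively. Missing values on post-dose AEs become severe and related, repeated events take the worst grade and the closest relationship, and an incomplete start date in the month or year of dosing is set to the first-dose date. Pre-dose-onset TEAEs are the one class of TEAE that receives the benign value. Safety is part of the primary objective, and in the extreme case a treatment-emergent serious event would be tabulated as mild and unrelated.

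**Working it through.** There is no stated figure to reproduce, because this is a check of one rule against another. I took each route into TEAE status under the general definition and applied 17.9 and 17.10 as written, assuming the AE keeps its original start date.

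| Route | Missing causality (17.10) | Missing severity (17.9) |
|---|---|---|
| (a) Onset on or after first dose | yes | severe |
| (b) Pre-dose onset, severity increases after dosing | no | mild, but rarely reachable |
| (c) Pre-dose onset, becomes serious after dosing | no | mild |
| Pre-dose onset, never treatment-emergent | no | mild |

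- **Route (a)** and the last row behave as intended.
- **Route (b)**: a TEAE with missing causality leaves the treatment-related table. The severity cell is nearly empty, because an increase in severity can normally be seen only when grades are recorded, and then there is nothing to impute.
- **Route (c)**: seriousness does not depend on a grade, so severity can be missing. The event is a TEAE and a TESAE, yet it would be tabulated as mild, and as not related if causality is also missing.

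**Scale.** Planned group sizes are 270 BOTOX and 90 placebo (Protocol 9.2, SAP 15.0).

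- One participant on BOTOX: 1/270 = 0.37 percentage points.
- One participant on placebo: 1/90 = 1.11 percentage points.

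The documents give no count of such events. A case needs onset between consent and dosing (screening is Day -14 to Day -1), worsening or seriousness after dosing, and a missing field. I assume 0 to 2 participants. Two in one arm would be 2/270 = 0.74 or 2/90 = 2.22 percentage points.

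**Direction between arms.** Suppose the same proportion r of each arm is affected. Expected counts are 270r and 90r, so BOTOX holds 270/(270 + 90) = 75% of them. The percentage in each arm falls by r, and the expected difference in rates is r − r = 0.

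**The case against.** Several points on the other side stand and limit the finding.

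- **Missing causality should be rare.** Protocol Appendix 2 obliges the investigator to assess the relationship for every AE, and for an SAE before it is first transmitted. A route (c) event with no causality would breach the protocol.
- **The retained start date is an inference.** Protocol 8.3.3 puts updates in the original eCRF, but no readable section says how the start date is handled when an AE worsens. Appendix 2 counts an exacerbation of a pre-existing condition as an AE. If sites enter a worsening as a new record with a post-dose onset, the present rules already give severe and yes.
- **The cycle 1 sentence is narrower.** Read literally, it may leave route (b) out of the cycle 1 tables, where BOTOX is compared with placebo. That limits the effect there, but it is itself an inconsistency to resolve.
- **Little is hidden.** Under SAP 10.2, overall TEAE incidence and the TESAE summary depend on neither field. All AEs are listed, with the gaps visible.

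A reader might also draw two stronger conclusions that the documents do not support. One is that any AE that worsens after dosing is imputed as mild. That fails for route (b), where grades are normally recorded. The other is that the rule favours BOTOX, because three quarters of such events would fall in that arm. That share is simply the 3:1 allocation. The rules cover both arms, the tables report percentages by arm, and equal rates give no expected distortion of the comparison.

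**Conclusion.** The mismatch is real but minor. As written, a TEAE with a pre-dose start date and missing causality is classed as not related, and a TEAE that qualified by becoming serious and has no grade is classed as mild. This runs against the SAP's own conservative convention and can only lower the related and severe counts, in whichever arm the event occurs.

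The expected size is 0 to 2 participants, at 0.37 percentage points each on BOTOX or 1.1 on placebo. Zero is plausible. That range is my assumption, and the finding also rests on the AE keeping its pre-dose start date, which Protocol 8.3.3 suggests but does not state. No efficacy analysis, sample size or alpha is touched. The case for changing the text is internal consistency at almost no cost.

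**What to change.** 1. **Set TEAE status first**, from non-missing data only: onset date, recorded change in severity, and seriousness. Without this step the severity rule would be circular, because status can itself depend on severity.
2. **SAP 17.10**: assign yes to any TEAE with missing causality, including one with pre-dose onset, and no to all other AEs.
3. **SAP 17.9**: assign severe to any TEAE whose post-dose severity is missing, including a pre-dose AE that became serious after dosing. Keep mild for AEs that are not treatment-emergent.
4. **SAP 10.2**: add an increase in severity to the cycle 1 TEAE sentence so that it agrees with the general definition above it.

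This wording gives the same answer whether sites update the original AE record or open a new one. The cost is a sentence or two in each of three SAP sections and a small programming change. Related or severe counts may come out slightly less favourable.
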